## 5.0. RESEARCH DESIGN, METHODS, AND PROCEDURES

**Conceptual Framework.** Our conceptual framework (Figure 1) is based on [name]'s Contextual Support Model of Music Therapy and further informed by Kazak's Pediatric Medical Traumatic Stress Model, which provides a useful heuristic for understanding short and long-term consequences of pediatric cancer treatment for parents and their child. In our conceptual framework, recurring events related to cancer treatment (i.e., hospitalizations, procedures) are viewed as potentially traumatic events. Parent appraisal of events as traumatic or not traumatic is influenced by pre-existing factors, which serve as antecedents in our study.

Published research indicates that higher parent and child distress during cancer treatment and survivorship is related to: 1) demographics (younger child/parent age, female parent gender, and lower socio-economic status/education), 2) higher parent/child distress with prior hospitalizations, and greater traumatic stress symptoms, and 3) disease and treatment characteristics (diagnosis, relapsed disease, greater treatment intensity).

Figure 1: Conceptual Framework

The AME directly targets the proximal mediators of child engagement and parent-child interaction, as well as distal mediators of perceived family normalcy, parent confidence (self-efficacy) about their ability to support their child during treatment, and independent music play between therapist-led sessions.

[figure not shown]
Our study examines proximal and distal mediators of the AME on outcomes for young children (emotional distress, physical symptom distress (exploratory), quality of life), parents (emotional distress, traumatic distress, quality of life), and family function. In addition, we examine moderators of the AME intervention on outcomes (child/parent distress with prior hospitalizations; child age). This study will allow us to determine *how* and *for whom* the intervention works, informing a subsequent trial to examine cumulative impact/efficacy of AME across repeated cancer treatment admissions to manage distress and prevent traumatic stress symptoms in survivorship. Findings will also have implications for use of the CSM-MT to guide development of active music interventions to manage treatment distress in other populations.

**Study Design.** This is a two-group, randomized, controlled trial. Children and one parent will be stratified and randomized in blocks of six to the AME intervention or attention control condition (see Study Schema). Child/parent dyads will be stratified by child age (preschoolers 3-5 yrs; school-agers 6-8 yrs). Both conditions are standardized and each group will receive three 45-minute sessions over 3 days. We chose a randomized, controlled trial over a single-group trial as a control group is optimal for ruling out confounding variables that may impact the relationships between the intervention, mediators, and outcomes. For example, a single-group trial requires a dose be measured to represent the intervention since the variable being mediated must have some variation. The dose may be impacted by several unknown factors that could make interpretation of results difficult. Our prior studies suggest that 1) a usual care condition would likely have high attrition and negatively affect study accrual, and 2) our audio-storybooks low dose condition was acceptable without behavioral benefits. Thus, we will use audio-storybooks as our attention control condition. The number of sessions and amount of contact time were selected based on average length of stay and findings from our preliminary studies which found immediate and longer-term (30 days post-intervention) benefit.

As in our preliminary studies, baseline data (Time 1) will be intervention intervention collected after consent. Time 2 data are collected post-Session 3. Parents/children are encouraged to use AME and low dose audio-storybooks activities between sessions and at home following discharge and self-reported frequency and duration of activities will be collected during sessions 2 and 3, and at T3 (30 days post-intervention). Data collection timelines are based on positive findings from our preliminary studies and inform our primary aims which examine mediation. Findings will inform a subsequent trial to examine long term benefits. See Study Schema for assessment timelines.

**Setting.** Young children (ages 3-8 years) and their parents will be recruited from three children's hospitals. These hospitals are in metropolitan areas that serve large catchment areas. All three sites are members of the Children's Oncology Group, which treats similar types of cancer diagnoses with similar therapeutic protocols. The inpatient hospital setting and outpatient hematology/oncology clinic will be used for delivery of intervention and attention control conditions; data collection will occur both in the clinic and in-patient setting. All sites have verified availability of dedicated, private space for these activities.

**Study Procedures.** Procedures mirror successful strategies used in Preliminary Study 3, and our current R01 music intervention study for adolescents/young adults undergoing high risk cancer treatment and their parent.

**Recruitment & Consent.** Children/parents will be recruited during a clinic visit. As with our previous/current studies, certified research coordinators will use the eligibility checklist to identify potential participants and notify the project manager. The project manager will then contact the child/parent, explain the study, and if they are interested, obtain written parent consent for themselves and their child and assent for children > 6 years, following human subjects review committee requirements.

**Data Collection & Randomization Procedures.** Following consent, the project manager will arrange a time for parents to complete baseline (T1) measures during a routine clinic visit, prior to their next scheduled chemotherapy admission. A trained evaluator will administer measures in a quiet/private setting and remain available for questions. The child/parent dyad will then be stratified by child age (preschoolers 3-5 years; school-agers 6-8 years) and randomized in blocks of six to the AME or attention control condition by our statistician. The PI or project manager will then immediately schedule Session 1. Only the project manager, PI, statistician, and intervener will know the child/parent dyad's randomization status. Evaluators will be blinded.

All study condition sessions will be video recorded to facilitate collection of child engagement and parent-child interaction data and monitor treatment fidelity. Sessions 1 and 2 are video recorded to desensitize children/parents to video recording; only Session 3 video data are analyzed for Aim 1. In our previous studies, video recording did not negatively affect participant accrual. An evaluator, blind to randomization status, will administer T2 measures after Session 3. Evaluators will administer T3 measures 30 days (+/- 7 days) post-intervention during a subsequent clinic visit or by telephone. Parent self-reports will be used to monitor use of study condition activities between sessions and between T2 and T3 data collections (Appendix 1).

**Study Condition Procedures.** Consistent with our other studies, we train music therapists to deliver both intervention and control conditions to minimize risk for unblinding evaluators to participant group assignment. Risk for experimental drift, bias, and diffusion will be addressed through four quality assurance monitoring procedures established in our previous trials. Children/parents randomly assigned to AME or attention control receive the same length of sessions (45 min.) and timing of contact (3 sessions, 3 consecutive days). Session 1 will occur within 24 hours of hospital admission.

Usual care at all three sites. Across all sites, chemotherapy is administered according to Children's Oncology Group protocol guidelines, ensuring consistency of treatment. Antiemetic regimens are similar across sites and tailored to patient-specific needs. We will document patient medications at baseline, during hospitalization (T2), and 30 days post-intervention (T3) and control for site in all analytic models.

Procedures. Following consent, the project manager will arrange a time for the parent to complete baseline measures during a routine clinic visit, prior to their next scheduled chemotherapy admission. Baseline measures will be completed in a private room in the outpatient clinic. A trained evaluator will administer the baseline measures and remain available for questions during measurement completion. The evaluator will immediately notify the project manager that baseline measures are completed. The child/parent dyad will then be randomly assigned to the AME or the attention control condition by the study statistician. The PI or project manager will then immediately notify the child/parent of their randomization status and schedule their first session with the intervener. Only the project manager, PI, statistician, and intervener will know the child/parent's randomization status.

AME Intervention. Parents/children randomly assigned to the AME intervention receive three, 45-minute sessions with the music therapist, delivered daily, for 3 consecutive days. Session 1 is delivered within 24 hours of hospital admission. AME intervention sessions are designed for delivery by a board-certified music therapist (MT-BC) who tailors music-based play experiences to encourage active engagement in and independent use of music play as a strategy to manage distress. During AME sessions, the music therapist provides children/parents repeated opportunities to experience competence, autonomy, and meaningful interactions through music-based play activities, and

provides support/education about ways music play can be used to manage distress and sustain a sense of family normalcy while hospitalized and as they transition home.

There are three components to the AME intervention: 1) therapist-led music-based play activities and sessions, 2) the music play resource kit (to promote independent music play), and 3) tip sheets for parent education and support that focus on why music play, how to use music play during hospitalization, and how to use music play during transition from hospital to home. During each session, the music therapist begins with a 5 minute introduction/assessment period, followed by a 30 minute music play session, and closes with a 10 minutes of parent education and tailored suggestions for using music play outside sessions.

The child/parent also receive a music play resource kit to use during and between therapist-led sessions. The kit includes: 1) a professional CD recording of music composed and/or arranged specifically for this project, 2) age-appropriate musical instruments and play materials that correspond with each activity, and 3) activity cards designed to give children/parents at-a-glance information on ways they can use their kit. Universal precautions and hospital sterilization protocols will be observed for the compact disc players, compact disc recordings, music play resource kits, and other study materials. Children receive their own music play resource kit to keep both during and after study completion.

**Attention Control (Audio-storybooks).** Parents/children randomly assigned to the audio-storybooks attention control condition will have the same length of sessions (45 minutes) and timing of contact (3 sessions, 3 consecutive days) as the AME intervention group. Session 1 is delivered within 24 hours of hospital admission. The audio-storybooks (ASB) condition is designed to control for attention from an intervener, shared parent-child experiences, and audio-visual stimulation. It offers parents/children opportunities to make choices and engage in an age-appropriate, non-music-based play activity. In each session children/parents will choose and listen to one of two illustrated children's books with audio-taped narration. Children/parents receive a kit that includes 3 audio-storybooks that they can keep. Universal precautions and hospital sterilization protocol will be observed for the compact disc players, compact disc recordings, audio-storybooks kit, and other study materials. Children receive their own audio-storybooks kit to keep both during and after study completion.

All study condition sessions will be video recorded to facilitate collection of behavioral outcome data and monitor treatment fidelity. Sessions 1 and 2 are video recorded to desensitize children/parents to video recording; only Session 3 video data are analyzed for Aims 1 and 2. In our previous studies, video recording did not negatively affect participant accrual or cause distress. An evaluator, blind to randomization status, will administer T2 measures after Session 3. Evaluators administer T3 measures 30 days (+/- 7 days) post-intervention during a subsequent clinic visit or by telephone. All evaluation sessions are audio-recorded to monitor evaluation fidelity.

**Treatment Fidelity Strategies.** Our team developed and published treatment fidelity strategies consistent with NIH Treatment Fidelity Workgroup recommendations to ensure treatment integrity, minimize experimental drift, and minimize contamination of the control group. Strategies include: 1) standardized intervention and control condition protocols, study manuals, and training; 2) self- and external monitoring of video-recorded intervention/attention control sessions; 3) self- and external monitoring of audio-recorded evaluation sessions; 4) quality assurance checklists to track protocol deviations; 5) intervener field notes to document duration and frequency (dose), and uptake of study conditions; 6) separate intervener/evaluator conference calls; and 7) weekly study administration team meetings to address any concerns.

**Sources of Materials.** All data will be collected solely for the purposes of this study. Parents will complete a set of study measures three times (baseline, post-session 3, and 30-days post-session 3). We estimate it will take the parent 30 – 45 minutes to complete measures.

All measures will be completed using paper/pencil administration. Once parents complete a set of measures our evaluators will directly enter data into RedCap, a HIPAA compliant web-based data

management system. Paper measures will be secured in a locked cabinet, in a locked office dedicated to our study.

Medical information will be obtained from chart reviews, relevant to diagnosis and treatments. These data will be obtained by our evaluators, all of whom are Children's Oncology Group Certified Research Associates.

Field notes on intervention and evaluation sessions will be completed by music therapist and evaluators using a password protected computers that are connected to a secure web-based server. All study related materials and forms are stored on HIPAA compliant encrypted data management server.

All intervention and attention control sessions will be video recorded, and all evaluation sessions audio recorded to facilitate collection of behavioral outcome data and to monitor fidelity.

A listing of specific measures can be found in Section B and in Appendix 1 of this application. Only the PI and the project coordinator will have access to subject identities; all raw data, including digital audio and video data will be stored according to Indiana University IRB requirements.

**Potential Risks.** Risks to child/parent participants are considered minimal and include: 1) breach of confidentiality; 2) increased fatigue for the child or parent as a result of participating in study session activities or completing measures; and 3) psychological discomfort for the parent when responding to evaluation questions.

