### **3.0. SAMPLE ELIGIBILITY CRITERIA**

**Child/Parent Inclusion Criteria and Rationale:** Children and parents/caregivers will be eligible if: 1) the child is 3 – 8 years of age at time of enrollment (intervention content is not age-appropriate for other children); 2) patients with an expected treatment course of at least 3 days to receive moderate to high intensity chemotherapy and/or radiation therapy either in-patient or outpatient (children receiving chemotherapy are at risk for high symptom distress; 3-day treatment course is required to deliver study conditions and contributes to sample homogeneity); and 3) one parent/caregiver ( $\geq 18$  years of age) can be present for all sessions (study targets both child and parent/caregiver).

**Child/Parent Exclusion Criteria and Rationale:** Children and parents/caregivers will be excluded if: 1) the child and/or parent/caregiver do not speak English or 2) the child has a significant cognitive impairment that might hinder participation (determination made in consultation with attending physician, oncologist, and parents).

**Sample Size.** We will recruit a total sample size of 184 child and parent/caregiver dyads (368 total) and assume 15% attrition in order to retain 156 child and parent/caregiver dyads (78 dyads/group) at Time 3.

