## 6.0. MEASURES AND DATA COLLECTION INSTRUMENTS

All measures reflect careful consideration of psychometric properties, sensitivity to change, and response burden. See Appendix 1 for measures and additional psychometrics.

Variable(s)	Measure	# Items	Reliability Evidence	Admin. Schedule	Completed By
Antecedent Factors					
Demographics -parent/child age, parent gender, SES, parent education	Family Information Form	3	N/A	T1	Parent
Prior Distress w/ Hospitalization -parent/child	Prior Illness Experiences Scale (PIES) Abbreviated PTSD checklist (PCL-S)	13 6	.78† .94†	T1 T1, T2, T3	Parent Parent
Disease Characteristics Treatment Characteristics	Diagnosis and Treatment Form Intensity of Treatment Rating Scale Medication Data Form	2 1 7	N/A .95* N/A	T3 T3 T1, T2, T3	Evaluator Oncologist Evaluator
Proximal Mediators					
Child Engagement Parent-Child Interaction	Behavioral Coding Form Behavioral Coding Form	N/A N/A	.85* .85*	Session 3 Session 3	Trained Coder Trained Coder
Distal Mediators					
Family Normalcy Perspective	Family Management Measure (FaMM) Family Life Difficulty Subscale	14	.90†	T1,T2,T3	Parent
Parent Self-Efficacy	Parental Beliefs Scale (PBS)	20	.85†	T1,T2,T3	Parent
Independent Music Play	Parent Report	2	N/A	Sessions 2/3; T2	Parent
Child Outcomes					
Child Emotional Distress	CHQ – Mental Health Subscale	16	.81†	T2, T3	Parent
Child Physical Symptom Distress	Edmonton Symptom Assessment System (ESAS)	3	.69-.80†	T1, T2, T3	Parent
Child Quality of Life	KINDL R	20	.89†	T1, T2, T3	Parent
Parent Outcomes					
Parent Emotional and Traumatic Stress Symptoms	Profile of Mood States-Short Form (POMS) Impact of Events Scale-Revised (IES-R)	37 22	.99** .84-.91†	T1,T2,T3 T1, T2, T3	Parent Parent
Parent Quality of Life	Index of Well-being	9	.93†	T1, T2, T3	Parent
Parent/Child Outcomes					
Family Function	(FACES II)	30	.90†	T1,T2,T3	Parent

†Cronbach's alpha; \*inter-rater reliability; \*\*correlation with POMS

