**Main analyses:** For analyses below we will analyze as randomized and attempt to collect outcome data on non-completers, following the intent-to-treat principle. For Aims 1 and 2, each outcome will be modeled separately. Also we will model T2 separately from T3. Thus, there will be a total of 12 models in Aim 1 (6 outcomes x two time points). In Aim 2, two outcomes will be examined and 3 potential moderators at two time points for a total of 12 (2 outcomes x 3 moderators x 2 time points) models. For Aim 1, our primary goal is to test mediation effects. Mediation effects will be estimated in an ANCOVA setting, fitting the appropriate mediation models using MPlus and then testing indirect effects using the percentile bootstrap approach to estimate the indirect effect. The multiple mediation model with three-path mediation effects specifies that the intervention will act through the proximal and distal mediator on the outcome and also have a direct effect on the outcome. Each outcome model will have 6 key predictors (intervention, two proximal mediators, 3 distal mediators), and control for T1, age (3-5 years vs. 6-8 years), site, and any imbalanced baseline covariates found above (allowing for up to 6 imbalances). Thus we will have up to 15 variables in any model. For Aim 2, we will test moderation effects by including the appropriate interaction terms of the potential moderator (dichotomized at the median) with the intervention indicator (AME vs. attention control) in our models. For all models in Aims 1 and 2, we will assess goodness-of-fit (GOF) using standard GOF measures (comparative fit index, root mean square error of approximation, and root mean square residual). For Aim 3, an exploratory aim, we will use ANCOVA to compare changes in child symptom distress at T2 and T3 between intervention and control groups. In light of positive findings, we next will explore models as in Aims 1 and 2 to assess for potential mediation and moderation effects for this outcome.

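### Inpatients and outpatients are both enrolled, but treatment setting is not a pre-specified covariate in the Aim 1 mediation models; adding it is a cheap improvement

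*Combined protocol and SAP*

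**What the plan says.** Section 3.0 makes children eligible for "chemotherapy and/or radiation therapy either in-patient or outpatient", with an expected course of at least 3 days at moderate to high intensity. Section 5.0 (Setting) confirms that both settings will be used: "The inpatient hospital setting and outpatient hematology/oncology clinic will be used for delivery of intervention and attention control conditions".

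The timing text refers only to admission. Under Study Condition Procedures, "Session 1 will occur within 24 hours of hospital admission". The AME and audio-storybook descriptions repeat it: "Session 1 is delivered within 24 hours of hospital admission". Baseline is placed before the next chemotherapy admission, and the medication text ties T2 to a hospital stay: "We will document patient medications at baseline, during hospitalization (T2").

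Independent play is encouraged outside the sessions: "Parents/children are encouraged to use AME and low dose audio-storybooks activities between sessions and at home following discharge". Section 6.0 schedules its measurement at "Sessions 2/3; T2".

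Section 7.0 (Main analyses) makes testing mediation the primary goal of Aim 1. Beyond the intervention and five mediators, the outcome models "control for T1, age (3-5 years vs. 6-8 years), site, and any imbalanced baseline covariates found above". Child age is the only stratification factor. Setting is not a stratum, a proposed moderator, a listed measure or a named covariate.

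**The concern.** An indirect effect multiplies the effect of AME on a mediator by the mediator's association with the outcome. Randomization supports the first part but not the second: dyads are not randomized to how much they play. A common cause of play and distress therefore biases the second part, even if that cause is perfectly balanced between arms.

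Setting is a credible candidate. Section 2.0 describes the play mediator as use while hospitalized, whereas an outpatient dyad may spend the time between sessions at home. The conceptual framework in Section 5.0 counts hospitalizations among potentially traumatic events, though it compares no settings.

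The provision for imbalanced covariates does not cover this. It is triggered by differences between arms, and the screen in Section 7.0 covers demographic and baseline outcome variables; setting is not clearly either. Site adjustment removes only between-site differences in setting.

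The most exposed path runs from independent play to the CHQ, a primary outcome, because the Section 6.0 table shows no T1 score for either. Direction is unknown. If outpatients play less and are less distressed, a beneficial play effect is masked; if they play more and are less distressed, it is inflated.

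**Working it through.** **The plan's own counts.** Six key predictors + T1 + age group + site (counted as one) + up to 6 imbalances = 15 variables, matching Section 7.0. Sample size: 156/0.85 = 183.5, rounded up to 184, matching Section 3.0. None of the 15 places is reserved for setting.

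**Assumed inputs (not in the documents).** Outpatient share p = 0.10 or 0.40; shift s = 0.3 or 0.5 within-setting SD in both mediator and outcome; within-setting mediator correlation r = 0.3 or 0.5; no site or T1 adjustment. Let v = s²p(1-p), the covariance that setting induces.

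**Bias in the play coefficient, joint five-mediator regression, setting omitted.**

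- All five mediators shifted equally: bias = v/(1+4r+5v).
- Only play shifted: bias = Vv/(1+Vv), where V = (1+3r)/((1-r)(1+4r)), which is 1.234 at r = 0.3 and 1.667 at r = 0.5.

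| s | p | v | all five, r=0.3 | all five, r=0.5 | play only, r=0.3 | play only, r=0.5 |
|---|---|---|---|---|---|---|
| 0.3 | 0.10 | 0.0081 | 0.0036 | 0.0027 | 0.0099 | 0.0133 |
| 0.3 | 0.40 | 0.0216 | 0.0094 | 0.0069 | 0.0260 | 0.0347 |
| 0.5 | 0.10 | 0.0225 | 0.0097 | 0.0072 | 0.0270 | 0.0361 |
| 0.5 | 0.40 | 0.0600 | 0.0240 | 0.0182 | 0.0689 | 0.0909 |

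The sign is positive if setting moves play and distress the same way, and negative if it moves them in opposite ways.

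**False positives.** Simulation with 78 dyads per arm, r = 0.3, a true play-to-outcome path of zero, and a percentile bootstrap 95% interval for (AME effect on play) × (play coefficient). With setting omitted, rejection is 1.9-5.8% in 15 of 16 scenarios. It reaches 9.0% in one: play only, p = 0.40, s = 0.5, AME effect on play 0.5 SD. With setting included, all 16 lie at 1.8-4.9%.

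**Masking.** Same simulation with a true path of -0.25, an AME effect on play of 0.5 SD, and both play and distress lower in outpatients. Detection without versus with setting:

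| s, p | play only, both arms | all five mediators |
|---|---|---|
| 0.3, 0.10 | 63.4 vs 65.4% (loss 2.0) | about 67 vs 68% (1) |
| 0.3, 0.40 | 58.1 vs 66.5% (8.4) | about 63 vs 67% (4) |
| 0.5, 0.10 | 56.0 vs 64.9% (8.9) | about 62 vs 66% (4) |
| 0.5, 0.40 | 43.4 vs 67.1% (23.7) | about 56 vs 66% (10) |

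If only play in the AME arm shifts, the loss is about 0-4 points in the first three scenarios and about 7 (26 vs 33%) in the last. In the play-only column the mean estimated path is -0.24, -0.22, -0.22 and -0.18. The closed form agrees: -0.25 + 0.0689 = -0.181 in the last row.

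**Inflation.** If play is instead higher in outpatients (play only), the estimated path runs from about -0.26 to -0.31.

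**Cost of the term.** Residual degrees of freedom go from 156 - 1 - 15 = 140 to 139. If setting has no effect, standard errors widen by √(140/139) = 1.004, about 0.4%.

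**The case against.** The case for treating this as negligible is substantial, and much of it stands.

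- **The large figure is a corner case.** A 24-point loss needs a 40% outpatient share, 0.5 SD shifts, and play alone affected equally in both arms. Control dyads receive no music kit, so there may be little control-arm music play to shift.
- **The simulated test is not the planned one.** Section 7.0 specifies three-path effects through proximal and distal mediators, while the simulation tests a two-path product. Its detection rates illustrate the mechanism and do not forecast this trial's power.
- **Planned adjustment is left out.** Site is in every model, and Section 7.0 says all models adjust for the baseline outcome. The Section 6.0 table lists the CHQ at T2 and T3 only. The two statements conflict and the documents do not settle it. POMS, family normalcy and self-efficacy do have T1 scores.
- **Setting is not the only candidate.** The conceptual framework links diagnosis, relapse and treatment intensity to distress, and none is a pre-specified covariate. The intensity and duration criteria also narrow the difference between settings.
- **Setting may be recoverable** from chart review, field notes or video.

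These points limit the size of the concern. They do not show that the planned covariates cover setting, and they identify no harm from adding it. A covariate recovered and chosen after outcomes are seen would be post hoc.

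**Conclusion.** The gap is real but modest, and worth closing because closing it costs so little. The bias of about 0.003-0.09, and the detection loss of roughly 0-10 points in most structures, rest on assumed outpatient shares and shifts, a two-path test, and no site or T1 adjustment. The 24-point loss is the worst case examined.

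Four stronger readings might be inferred, and the documents do not support them:

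- **The trial's treatment comparison is biased.** It is not: randomization balances setting between arms on average, so total effects and AME-to-mediator effects are unaffected.
- **Aim 1 will produce false mediation findings.** Under the assumptions used, false positives rise noticeably in only one of 16 scenarios, and the direction of any bias is unknown.
- **Outpatients cannot receive Session 1 under the protocol.** The text lacks a time anchor for them, but delivery in the outpatient clinic is explicit, and the study manuals are not among the documents supplied. This is a wording gap.
- **A setting term would make the mediator paths unconfounded.** It would not: diagnosis and treatment intensity would remain as possible common causes.

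**What to change.** Record planned treatment setting (inpatient or outpatient) before randomization, if no form already holds it. Name it in Section 7.0, beside site and age group, as a covariate in both the mediator and the outcome equations of the Aim 1 models. The cost is at most one form field and one degree of freedom per equation: 15 variables become 16, residual degrees of freedom fall from 140 to 139, and the sample size stays at 184 dyads.

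As a wording clarification only, time Session 1 from hospital admission or, for a child who is not admitted, from the first outpatient treatment day of the qualifying course, and word the baseline deadline to match. While editing, state whether the CHQ is collected at T1, so that Sections 6.0 and 7.0 agree.
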